7.0 TRIAL PROCEDURES

7.1 Trial Procedures

The Trial Flow Chart - Section 6.0 summarizes the trial procedures to be performed at each visit. Individual trial procedures are described in detail below. It may be necessary to perform these procedures at unscheduled time points if deemed clinically necessary by the investigator.

Furthermore, additional evaluations/testing may be deemed necessary by the investigator and or the Sponsor for reasons related to subject safety. In some cases, such evaluation/testing may be potentially sensitive in nature (e.g., HIV, Hepatitis C, etc.), and thus local regulations may require that additional informed consent be obtained from the subject. In these cases, such evaluations/testing will be performed in accordance with those regulations.

7.1.1 Administrative Procedures

7.1.1.1 Informed Consent

The investigator or qualified designee must obtain documented consent from each potential subject or each subject's legally acceptable representative prior to participating in a clinical trial or Future Biomedical Research.

7.1.1.1.1 General Informed Consent

Consent must be documented by the subject's dated signature or by the subject's legally acceptable representative's dated signature on a consent form along with the dated signature of the person conducting the consent discussion.

A copy of the signed and dated consent form should be given to the subject before participation in the trial.

The initial informed consent form, any subsequent revised written informed consent form and any written information provided to the subject must receive the IRB/ERC's approval/favorable opinion in advance of use. The subject or his/her legally acceptable representative should be informed in a timely manner if new information becomes available that may be relevant to the subject's willingness to continue participation in the trial. The communication of this information will be provided and documented via a revised consent form or addendum to the original consent form that captures the subject's dated signature or by the subject's legally acceptable representative's dated signature.

Specifics about a trial and the trial population will be added to the consent form template at the protocol level.

The informed consent will adhere to IRB/ERC requirements, applicable laws and regulations and Sponsor requirements.

7.1.1.1.2 Consent and Collection of Specimens for Future Biomedical Research

The investigator or qualified designee will explain the Future Biomedical Research consent to the subject, answer all of his/her questions, and obtain written informed consent before performing any procedure related to the Future Biomedical Research sub-trial. A copy of the informed consent will be given to the subject.

7.1.1.2 Inclusion/Exclusion Criteria

All inclusion and exclusion criteria will be reviewed by the investigator or qualified designee to ensure that the subject qualifies for the trial.

7.1.1.3 Subject Identification Card

All subjects will be given a Subject Identification Card identifying them as participants in a research trial. The card will contain trial site contact information (including direct telephone numbers) to be utilized in the event of an emergency. The investigator or qualified designee will provide the subject with a Subject Identification Card immediately after the subject provides written informed consent.

The subject identification card also contains contact information for the emergency unblinding call center so that a health care provider can obtain information about trial medication/vaccination in emergency situations where the investigator is not available.

7.1.1.4 Medical History

A medical history will be obtained by the investigator or qualified designee. Medical history will include all active conditions, and any condition diagnosed within the prior 10 years that are considered to be clinically significant by the investigator. Details regarding the disease for which the subject has enrolled in this trial will be recorded separately and not listed as medical history.

Prior acute or chronic GVHD, maximum grade, and dates will be collected.

7.1.1.5 Prior and Concomitant Medications Review

7.1.1.5.1 Prior Medications

The investigator or qualified designee will review prior medication use, including any protocol-specified washout requirement, and record prior medication taken by the subject within 28 days before starting the trial. Treatment for the disease for which the subject has enrolled in the study will be recorded separately and not listed as a prior medication.

7.1.1.5.2 Concomitant Medications

The investigator or qualified designee will record medication, if any, taken by the subject during the trial through the Safety Follow-up visit. Record all medications taken for SAEs and ECIs as defined in Section 7.2.

7.1.1.5.3 Prior Cancer Treatment Details

The investigator or qualified designee will review all prior cancer treatments including systemic treatments, prior transplantation, radiation, and surgeries and record in the trial database.

7.1.1.5.4 Subsequent Antineoplastic Therapy

The investigator or qualified designee will review all new antineoplastic therapy initiated after the last dose of trial treatment. If a subject initiates a new antineoplastic therapy within 30 days after the last dose of trial treatment, the 30 day Safety Follow-up visit must occur before the first dose of the new therapy. Once new antineoplastic therapy has been initiated the subject will move into survival follow-up.

Collect transplant parameters after study treatment to include the conditioning regimen, date, and type of transplant.

7.1.1.6 Assignment of Screening Number

All consented subjects will be given a unique screening number that will be used to identify the subject for all procedures that occur prior to randomization or treatment allocation. Each subject will be assigned only one screening number. Screening numbers must not be re-used for different subjects.

Any subject who is screened multiple times will retain the original screening number assigned at the initial screening visit.

Specific details on the screening visit requirements (screening/rescreening) are provided in Section 7.1.5.1.

7.1.1.7 Assignment of Treatment/Randomization Number

All eligible subjects will be allocated, by non-random assignment, and will receive a treatment/randomization number. The treatment/randomization number identifies the subject for all procedures occurring after treatment allocation/randomization. Once a treatment/randomization number is assigned to a subject, it can never be re-assigned to another subject.

A single subject cannot be assigned more than 1 treatment/randomization number.

7.1.1.8 Trial Compliance (Medication/Diet/Activity/Other)

Interruptions from the protocol specified treatment (for 12 weeks between pembrolizumab doses due to toxicity) require consultation between the investigator and the Sponsor and written documentation of the collaborative decision on subject management.

Administration of trial medication will be witnessed by the investigator and/or trial staff. The total volume of trial treatment infused will be compared to the total volume prepared to determine compliance with each dose administered.

The instructions for preparing and administering pembrolizumab will be provided in the Pharmacy Manual.

7.1.2 Clinical Procedures/Assessments

7.1.2.1 Oncologic Disease Details

The investigator or qualified designee will obtain prior and current details regarding oncologic disease status.

7.1.2.2 Adverse Event Monitoring

The investigator or qualified designee will assess each subject to evaluate for potential new or worsening AEs as specified in the Trial Flow Chart and more frequently if clinically indicated. Adverse experiences will be graded and recorded throughout the study and during the follow-up period according to NCI CTCAE Version 4.0 (see Section 12.6). Toxicities will be characterized in terms regarding seriousness, causality, toxicity grading, and action taken with regard to trial treatment.

All AEs of unknown etiology associated with pembrolizumab exposure should be evaluated to determine if it is possibly an event of a potentially immunologic etiology (irAE). See Section 7.2 regarding the identification, evaluation, and management of AEs of a potential immunological etiology.

Please refer to Section 7.2 for detailed information regarding the assessment and recording of AEs.

7.1.2.3 Electrocardiogram

A standard 12-lead electrocardiogram (ECG) will be performed using local standard procedures at screening. Clinically significant abnormal findings should be recorded as medical history.

7.1.2.4 Physical Exam

7.1.2.4.1 Full Physical Exam

The investigator or qualified designee will perform a complete physical exam during the screening period. Clinically significant abnormal findings should be recorded as medical history. A full physical exam should be performed during screening (height need be taken at screening only) and repeated as per the frequency defined in the Study Flow Chart. After the first dose of trial treatment new clinically significant abnormal findings should be recorded as AEs.

7.1.2.4.2 Directed Physical Exam

For cycles that do not require a full physical exam per the Trial Flow Chart, the investigator or qualified designee will perform a directed physical exam as clinically indicated prior to trial treatment administration. New clinically significant abnormal findings should be recorded as AEs.

7.1.2.5 Vital Signs

The investigator or qualified designee will take vital signs at screening, prior to the administration of each dose of trial treatment and at treatment discontinuation as specified in the Trial Flow Chart (Section 6.0). Vital signs should include temperature, pulse, respiratory rate, weight and blood pressure. Height will be measured at screening only.

7.1.2.6 Eastern Cooperative Oncology Group (ECOG) Performance Status

The investigator or qualified designee will assess ECOG status (see Section 12.5) at screening, prior to the administration of each dose of trial treatment and discontinuation of trial treatment as specified in the Trial Flow Chart.

7.1.2.7 Assessment of Disease and Tumor Imaging

7.1.2.7.1 Tumor Imaging and Criteria for Assessment of Disease

The process for image collection and transmission to the independent central imaging vendor can be found in the Site Imaging Manual. Independent central review based on IWG response criteria (Cheson, 2007 [1]) will be used to determine subject eligibility.

The central imaging vendor will receive all CT/PET images from the sites including baseline images and will confirm eligibility. **Eligibility will be based on the independent central review assessment, rather than site assessment. Expedited confirmation of measurable disease as determined by central review will be communicated to the site.**

Anti-tumor activity of pembrolizumab by CT/PET will be evaluated using the following criteria:

- PMBCL: IWG response criteria (Cheson, 2007 [1]) See Section 12.7.
- RS: IWG response criteria (Cheson, 2007 [1]) with special considerations for RS (Section 12.7). In subjects with rrRS, assessment of disease in the bone marrow will be limited to RS lymphoma.

The IWG will be applied by the independent central imaging vendor as the primary measure for eligibility, assessment of tumor response, and date of disease progression. CT/PET imaging showing subject's eligibility should be submitted to the central imaging vendor immediately. The site will be notified if the independent central review confirms eligibility. Additionally, the investigator will apply the IWG response criteria for assessment of disease response and disease progression. In addition, assessment of lymphoma B symptoms should occur with each lymphoma disease response assessment.

In subjects with RS, assessment of disease in the bone marrow will distinguish changes due to RS or transformed lymphoma from changes due to the pre-existing CLL. RS subjects may be assessed as showing radiographic CR if all lesions resolve on anatomic imaging, or if all remaining lesions show PET avidity lower than normal liver tissue, consistent with complete disappearance of fluorodeoxyglucose (FDG)-avid disease. If radiographic CR is observed (no evidence of active disease on imaging), a final response determination of CR requires marrow clearance of RS (as determined by marrow biopsy and aspirate), as well as

disappearance of other clinical evidence of disease (such as physical exam findings). If the bone marrow is indeterminate by morphology, immunohistochemistry should be negative for RS. Residual underlying CLL may persist in node and/or marrow and still qualify as CR, denoting complete response of RS to pembrolizumab. Additional node biopsies for RS should be considered in the presence of enlarging lymph nodes to determine if due to underlying CLL or RS.

Anti-tumor activity of pembrolizumab will also be evaluated by independent central review as part of the exploratory analyses using the Lugano Classification (Cheson, 2014 [2]), see Section 12.8.

7.1.2.7.2 Disease Assessment of Immunotherapeutic Agents

Immunotherapeutic agents such as pembrolizumab may produce antitumor effects by potentiating endogenous cancer-specific immune responses, which may be functionally anergic. The response patterns seen with such an approach may extend beyond the typical time course of responses seen with cytotoxic agents, and can manifest a clinical response after an initial increase in tumor burden or even the appearance of new lesions. Standard response assessment criteria may not provide a comprehensive response assessment of immunotherapeutic agents such as pembrolizumab. Therefore in the setting where a subject assessment shows unconfirmed PD by investigator assessment, study drug may be continued upon Sponsor consultation, if the investigator considers the subject is deriving clinical benefit and providing subsequent radiographic imaging shows evidence of reduction or stabilization in tumor burden from the prior time point where initial unconfirmed PD was observed. If repeat imaging shows a reduction or stabilization in the tumor burden compared to the initial scan demonstrating PD, treatment may be continued/resumed. If repeat imaging confirms PD by investigator assessment, subjects will be discontinued from study therapy. Imaging should occur at any time where there is clinical suspicion of progression.

7.1.2.7.3 Initial Disease Assessment

Initial disease assessment or tumor imaging must be performed within 28 days prior to the first dose of trial treatment. The site study team must review pre-trial images to assess if the subject has measurable disease as defined in the inclusion criteria and submit CT/PET imaging showing subject's eligibility to the central imaging vendor immediately for confirmation. The site will be notified if the independent central review confirms eligibility as defined in the inclusion criteria.

Disease assessments or scans performed as part of routine clinical management are acceptable for use as the screening scan if they are of diagnostic quality and performed within 28 days prior to the first dose of trial treatment. CT and PET should be used throughout the study as stated in section 7.1.2.7.4 below. For lymphomas that are not FDG-avid at screening, PET does not need to be repeated in follow-up assessments.

7.1.2.7.4 Disease Response Assessments/Imaging During the Trial

Following screening, disease response assessments will occur at Week 12 (± 7 days) and every 12 weeks (± 7 days) as detailed in the Trial Flow Chart in Section 6.0. The first

assessment may be performed earlier than 12 weeks if, in the opinion of the investigator, the subject is clinically progressing.

Imaging assessments should be performed (every 12 weeks from the first dose of study medication). There is a ± 7 day window for assessments performed after entry in the study. If PET and CT scan at Screening are negative for disease involvement in the neck, subsequent CT scans may not include neck. If PET or CT scans at Screening are positive for disease involvement of the neck, subsequent CT scans must include neck. Following screening, CT scans should be repeated every 12 weeks for subsequent assessments. PET should be repeated at Week 12, Week 24, or to confirm CR and as clinically indicated. PET to confirm PD is strongly encouraged, but not required, if CT clearly demonstrates PD. Disease assessments and imaging should not be delayed for delays in cycle starts.

Disease assessments and imaging should continue to be performed until documented disease progression by investigator assessment, the start of new anti-cancer treatment, withdrawal of consent, death, or the end of the study, whichever occurs first.

During Second Course, imaging should continue to occur every 12 weeks (+/- 7 days) following the same parameters listed above.

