- a. In subjects who discontinue study therapy without documented disease progression, every effort should be made to continue monitoring their disease status by radiologic imaging every 12 weeks (\pm 7 days) until (1) the start of new anti-cancer treatment, (2) documented disease progression by investigator assessment, (3) death, or (4) the end of the study, whichever occurs first.
- b. After the start of new anti-cancer treatment or documented disease progression by investigator assessment, the subject will transition to the Survival Follow-up and should be contacted by telephone (or in person if recent contact for other purposes during window) approximately every 12 weeks to assess survival status. Updated survival status may be requested by the Sponsor at any time during the course of the study. Upon Sponsor notification, all subjects who do not/will not have a scheduled study visit or study contact during the Sponsor-defined time period will be contacted for their survival status (excluding subjects who have a death event previously recorded).
- c. If subjects have stable disease, partial remission, or complete response they should continue on every 12 week (\pm 7 days) assessment schedule as described in section 7.1.2.7.4. Imaging should occur at any time where there is clinical suspicion of progression.
- d. In subjects with an unconfirmed PD assessment who continued study therapy, a radiological assessment should be performed 12 weeks (\pm 7 days) later or at the time of treatment discontinuation. If previous scan was obtained within 4 weeks prior to the date of discontinuation, then a repeat scan at treatment discontinuation isn't mandatory. However, imaging should occur at any time where there is clinical suspicion of progression.
- e. For women of reproductive potential, a urine pregnancy test should be performed within 72 hours prior to each cycle of trial treatment. If urine pregnancy results cannot be confirmed as negative, a serum pregnancy test performed by the local study site laboratory will be required. Pregnancy tests (serum and/or urine tests) should be repeated if required by local guidelines.

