8.4.1 Efficacy Endpoints

Efficacy endpoints that will be evaluated are listed below, followed by the descriptions of the derivations of selected endpoints.

The primary efficacy endpoint is the ORR for each cohort, defined as the proportion of subjects in the analysis population who have CR or PR at any time during the study, prior to disease progression. For rrPMBCL, response assessment will be based on IWG criteria (Cheson, 2007 [1]) using independent central review. For subjects with rrRS, IWG criteria with special considerations for RS will be used (Section 12.7). A secondary efficacy endpoint is ORR based on investigator assessment.

Other secondary efficacy endpoints include: (1) PFS, defined as the time from first dose of pembrolizumab to the first documented disease progression or death due to any cause, whichever occurs first; (2) DOR, defined as time from first response (CR, PR) to disease progression in subjects who achieve a PR or better, (3) DCR, defined as the proportion of subjects in the analysis population who have CR, PR, or SD at any time during the study prior to disease progression and (4) OS, defined as time from first dose to date of death.

PFS, DOR, and DCR will be based both on central review (primary) and investigator assessment (secondary).

Exploratory efficacy endpoints include ORR, PFS, DOR, and DCR, incorporating response assessments for subjects continuing pembrolizumab treatment after initial progression. An additional exploratory endpoint is the ORR based on the Lugano classification [2] using independent central review.

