8.6 Statistical Methods

8.6.1 Statistical Methods for Efficacy Analyses

A summary of the primary analysis strategy for the primary and secondary efficacy endpoints is provided in [Table 10](#) below. The primary evaluation will be by central review for ORR, DCR, PFS, and DOR.

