8.6.1.3 Progression-Free Survival

The non-parametric Kaplan-Meier method will be used to estimate the PFS curve.

Since disease progression is assessed periodically, PD can occur any time in the time interval between the last assessment where PD was not documented and the assessment when PD is documented. For the primary analysis, for the subjects who have PD, the true date of disease progression will be approximated by the date of the first assessment at which PD is objectively documented per IWG criteria, regardless of discontinuation of study drug. Death is always considered as a confirmed PD event.

In order to evaluate the robustness of the PFS endpoint, we will perform two sensitivity analyses with a different set of censoring rules. The first sensitivity analysis is the same as the primary analysis except that it censors at the last disease assessment without PD when PD or death is documented after more than one missed disease assessment. The second sensitivity analysis is the same as the primary analysis except that it considers discontinuation of treatment or initiation of new anticancer treatment, whichever occurs later, to be a PD event for subjects without documented PD or death. The censoring rules for primary and sensitivity analyses are summarized in [Table 9](#).

Table 9 Censoring rules for Primary and Sensitivity Analyses of Progression-Free Survival

Situation	Primary Analysis	Sensitivity Analysis 1	Sensitivity Analysis 2
No progressive disease (PD) and no death; new anticancer treatment is not initiated	Censored at last disease assessment	Censored at last disease assessment	Censored at last disease assessment
No PD and no death; new anticancer treatment is initiated	Censored at last disease assessment before new anticancer treatment	Censored at last disease assessment before new anticancer treatment	Progressed at date of new anticancer treatment
PD or death documented after ≤ 1 missed disease assessment	Progressed at date of documented PD or death	Progressed at date of documented PD or death	Progressed at date of documented PD or death
PD or death documented after ≥ 2 missed disease assessments	Progressed at date of documented PD or death	Censored at last disease assessment prior to the ≥ 2 missed disease assessment	Progressed at date of documented PD or death

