8.6.1.4 Duration of Response

DOR is defined, only for the subgroup of subjects who achieve CR or PR, as the time from start of the first documentation of objective tumor response (CR or PR) to the first documentation of tumor progression or to death due to any cause, whichever comes first. The analysis will consist of Kaplan-Meier estimates. Duration of response data will be censored on the date of the last disease assessment documenting absence of PD for subjects who do not have tumor progression and are still on study at the time of an analysis, are given antitumor treatment other than the study treatment, or are removed from study prior to documentation of tumor progression.

An exploratory analysis will be performed including response duration for those subjects who continue to receive pembrolizumab following progression and later achieve CR or PR.

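### Scheduled imaging ends at investigator-assessed progression, but the main PFS and DOR use central review: subjects with investigator PD and no central PD are censored or counted late, and no planned analysis isolates them

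*Combined protocol and SAP*

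**What the plan says.** **When scanning stops.** Section 7.1.2.7.4: "Disease assessments and imaging should continue to be performed until documented disease progression by investigator assessment". New anticancer treatment, withdrawal of consent, death and study end also stop it. Section 6.1, footnote a, gives the same rule for subjects off treatment ("2) documented disease progression by investigator assessment"), and Section 7.1.5.4 repeats it. None of these places requires central verification of PD.

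**Who reads the endpoint.** Section 7.1.2.7.1 has the central vendor apply the IWG criteria "as the primary measure for eligibility, assessment of tumor response, and date of disease progression". Section 8.6.1: "The primary evaluation will be by central review for ORR, DCR, PFS, and DOR". Investigator-assessed PFS and DOR are planned as secondary versions (Section 8.4.1, Table 10).

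**Repeat scan.** Section 7.1.2.7.5 provides repeat imaging 4–6 weeks after first progression in clinically stable subjects and exempts unstable ones. Section 6.1, footnote d, gives 12 weeks, or the time of discontinuation, for unconfirmed PD with continued therapy.

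**PFS censoring (Section 8.6.1.3, Table 9).** With no PD, no death and no new therapy, the entry in all three columns is "Censored at last disease assessment". If new therapy was started, the primary column reads "Censored at last disease assessment before new anticancer treatment". Death is an event in the primary analysis, even after two or more missed assessments.

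**DOR censoring (Section 8.6.1.4).** "Duration of response data will be censored on the date of the last disease assessment documenting absence of PD". This covers progression-free subjects who receive other antitumor treatment or leave the study. Death is an event. No DOR sensitivity analysis is specified.

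**The concern.** One reader decides when scanning stops and another decides whether an event occurred. When the investigator calls PD and central review does not, no later scheduled scan can supply a central PD date. The subject leaves the central risk set because a physician judged that treatment had failed, so the censoring is informative.

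PFS and DOR are key secondary endpoints in Table 8. The trial has no control arm to share the bias, and the repeated efficacy updates described under Table 10 would each carry it. The DOR set is small: with 50 treated subjects and the 35% ORR used for power, there are about 0.35 × 50 = 17.5 responders, so three or four discordant cases are already about 20% of them.

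**Working it through.** **The plan's own figure.** No figure is given for PFS, DOR or reader discordance. The only power statement concerns ORR. With 14 responders of 50 required, one-sided alpha is 0.0132 and power at 35% is 88.4%, which agrees with Table 11 and with the stated minimum of 88%. Neither figure uses PFS or DOR.

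**Inputs for PFS.** The 12-week scan interval and the Table 9 rules come from the plan. Assumed: exponential PFS with median 5 months, median survival after PD of 6 months, follow-up of 12–30 months, no further scan after investigator PD, every investigator PD a true failure, and a share d of investigator PDs not called centrally.

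**Step 1, reference (every investigator PD counts).** The interval is 12/4.345 = 2.76 months. The probability of passing one interval is p = 0.5^(2.76/5) = 0.682, so the per-scan hazard is h = 0.318. Two scans fall before 6 months and four before 12 months: p² = 46.5% and p⁴ = 21.6%.

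**Step 2, upper limit (every discordant subject censored at the scan).** The estimate is (1 − h(1 − d))^k, with k = 2 or 4.

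**Step 3, Table 9 primary rule (every later death is an event).** By simulation, about 74% of discordant subjects die before the cut-off and become late events.

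| d | 6 months: step 2 | 6 months: step 3 | 12 months: step 2 | 12 months: step 3 |
|---|---|---|---|---|
| 0% | 46.5% | 46.5% | 21.6% | 21.6% |
| 10% | 50.9% | 50.6% | 25.9% | 24.9% |
| 20% | 55.6% | 54.8% | 30.9% | 28.4% |
| 30% | 60.4% | 58.9% | 36.5% | 31.7% |

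Under the Table 9 rule the rise is about 4, 8 and 12 points at 6 months and 3, 7 and 10 points at 12 months.

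**Step 4, median.** The reference estimate at the week-24 scan (5.5 months) is 46.5%, just under one half. A small upward shift therefore moves the median towards the week-36 scan (8.3 months). That is largely a scan-grid effect, and the landmark rates are the better measure.

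**Step 5, DOR.** This is a separate simulation. Assumed: time to failure with latent median 4, 6 or 9 months, median survival after PD of 4 or 8 months, 18 months of accrual, a cut-off 12 months after last entry, and 60% of discordant subjects starting new therapy and censored for it. The 12-month estimates at d = 20% are:

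| Latent median / survival after PD (months) | Reference | DOR rule | Rise (points) |
|---|---|---|---|
| 4 / 4 | 14.8% | 21.7% | 6.9 |
| 4 / 8 | 14.7% | 22.8% | 8.1 |
| 6 / 4 | 28.0% | 35.5% | 7.5 |
| 6 / 8 | 27.9% | 36.4% | 8.5 |
| 9 / 4 | 42.7% | 49.5% | 6.8 |
| 9 / 8 | 42.7% | 50.4% | 7.7 |

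At d = 10% the rise is about 3–4 points and at 30% about 11–13. The Table 9 PFS rule gives 4–8 points in the same scenarios at 20%. DOR is affected more because new therapy censors a subject whose later death would count in PFS.

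**The case against.** - **Further scans exist.** A reader might infer that nothing is imaged after investigator PD. Section 7.1.2.7.5 and footnote d do not support that: many subjects get another scan, and the central vendor receives all images. This narrows the gap, and the no-further-scan assumption above overstates it. It does not close the gap, because unstable subjects are exempt and central review may not call PD on the later scan either. The two timings for the repeat scan also need to be reconciled.
- **Deaths count.** A reader might infer that these subjects are all censored as they fail. For PFS the plan does not support that: survival follow-up continues after PD and new therapy (Section 7.1.5.4.2), so most become events. The events are late, however, and the estimate still rises.
- **Sensitivity Analysis 2.** A reader might infer that it recovers only subjects who start new therapy. Table 9 reads that way, but the text of Section 8.6.1.3 takes the later of treatment discontinuation and new therapy as a PD event, which would capture subjects taken off drug. The two conflict. Even on the wider reading the analysis would also count stops for other reasons, and it covers PFS only.
- **Investigator-assessed PFS and DOR are planned.** They count these events, but they change the reader for every subject and so cannot show how far the central estimate depends on the discordant ones.
- **Investigators may overcall.** Section 7.1.2.7.2 expects some apparent early progression to stabilise or shrink. This stands: the bias is then smaller, and counting investigator PD would bias the estimate downward.
- **PFS and DOR are descriptive.** Also true. The only hypothesis concerns ORR.

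**Conclusion.** The mismatch between the investigator-based stopping rule and the centrally read endpoints is real. It biases central PFS and DOR upward to the extent that investigator PD is true failure. On the stated assumptions, 20% discordance adds about 8 points to 6-month PFS and about 7 to 12-month PFS, and under separate assumptions about 7–9 points to 12-month DOR. The point is strongest for DOR, which has no sensitivity analysis under central review.

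The size is illustrative. The documents give no discordance rate, and confirmatory scans or investigator overcalling would reduce it. A reader might take from the simulation that median PFS is inflated from 5.5 to 8.3 months; that jump is mostly one scan interval and should not be quoted as the effect. The ORR test, its boundaries and its power are unaffected.

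**What to change.** 1. Add a supportive sensitivity analysis for central PFS (Table 9) and central DOR (Section 8.6.1.4): where the investigator recorded PD and central review did not, count an event at the investigator PD date. Label it a conservative bound, because investigator overcalls bias it downward. Report how often the two readers agree on PD and on its date.
2. Reconcile Sensitivity Analysis 2, so that the text of Section 8.6.1.3 and Table 9 agree on whether stopping treatment without new therapy is a PD event.

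Cost: one more analysis per endpoint on data already collected, with no extra scans and no change to patient management. The sensitivity figures will look less favourable than the main ones.
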